A randomized trial comparing the adenoma detection rates between EndoRings colonoscopy (EC) and Standard colonoscopy (SC).

NCT03418662

A randomized trial comparing the adenoma detection rates between EndoRings colonoscopy (EC) and Standard colonoscopy (SC).

Primary Investigator:

[name]
Indiana University Hospital
Indianapolis, IN 46202

Introduction:

During a standard colonoscopy, the folds within the colon can negatively impact the endoscope's view, reducing the ability to detect polyps. In order to help remedy this issue, there is a new provisional device called **ENDORINGS™**. This device is a short silicone rubber tube with flexible circular wings mounted on the tip of the colonoscope to facilitate endoscopic therapy. By flattening the colonic folds during withdrawal, this device could help to keep a suitable depth of the endoscope's view field and, in turn, could prove to increase the adenoma detection rate. The EndoRings is designed to fit specific endoscopes (as designated on the packaging), supplied sterile and is single use only. This device could prove to be an improvement of the current design.

Methods:

Colonoscopies will be performed by [name] and a number of sub-investigators. Data that will be assessed from each colonoscopy include the following:

1. APC (Adenoma per Colonoscopy)
2. Total adenomas detected
3. Total polyps detected
4. Polyp detection rate (PDR)
5. PPC (Polyp per Colonoscopy)
6. Effect on re-scope intervals
7. Cecal intubation rate
8. Comparison of the time required to reach the cecum
9. Comparison of the withdrawal and total procedure time
10. Effect of endoscopist experience on potential gain from using EndoRings
11. Patient comfort score
12. Problems encountered with equipment
 - Slippage of Endorings™
 - Difficulty intubating with Endorings™

Objectives:

The primary endpoint of the study will be the adenoma detection rate of the EndoRings Colonoscopy (EC) compared to that of the Standard Colonoscopy (SC). Complications will be recorded, but the study will not be powered for complications.

The study will help to establish a device that will result in improved adenoma detection rates when compared to a standard colonoscope.

Criteria:

Inclusion Criteria:

- Age \geq 18
- Screening or Surveillance Colonoscopy
- Able to provide written informed consent

Exclusion Criteria:

- Prior history of surgical resection of the large intestine
- Known narrow colon or colon stenosis
- Personal history of Colorectal cancer
- History of Inflammatory bowel disease
- Familial adenomatous polyposis syndrome (FAP)
- Hyperplastic polyposis syndrome
- Referral for incomplete colonoscopy or polyp clearance

Randomization:

Once a patient has been screened to ensure inclusion and exclusion criteria have been met and has provided consent for participation in the study, the subject will be randomized in a 1:1 ratio. Randomization outcomes include the Standard Colonoscopy or the EndoRings Colonoscopy.

Statistical Analysis & Sample Size:

The primary analysis compares the adenoma detection rate between the EC group and the SC group. It is assumed that the proportion of patients with at least one adenoma would be 25% with SC and 35% with EC colonoscopy.

A two group Chi-Square test with a 0.05 one-sided significance level will have 80% power to detect a difference of 10% ADR between the two groups (odds ratio of 1.615) when the sample size in each group is 259, a total sample size of 518 subjects.

The final sample size will be 569 after adding the 10% expected drop-out rate.

Interim analysis will be performed after the 200th patient is enrolled to assess device performance and protocol amendment.

Data Integrity and Safety

All paper charts pertaining to the patient will be kept under lock and key in coordinators office away from the endoscopy area. The data entry will be performed into an excel file which will be stored on an internal network drive with encryption and password security. Only approved personnel by the IRB will have access to the file storage. This file will also not have any identifiable patient information. A study log with the identifiable information will be kept in a separate folder to enable the investigators to assist in any research audit. No procedural data except the date of examination will be entered into this log.

Any subject who wishes to withdraw from this investigation on his/her own accord and for whatever reason is entitled to do so without obligation and prejudice to further treatment. In addition, the Investigator may decide for reasons of medical prudence, to withdraw a subject. In either event, the Investigator will clearly document the date and reason(s) for the subject's withdrawal from this investigation in the CRF and should indicate whether or not he considers it was related to the study interventions.

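### Operators may differ in skill, but the plan states no endoscopist stratification, does not fix the operator before allocation, and tests ADR without an endoscopist term

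*Combined protocol and SAP*

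**What the plan says.** The combined protocol and SAP touches on operators in three places.

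- **Methods.** The procedures are done by the lead investigator "and a number of sub-investigators". Number, caseload and experience are not given. Item 10 of the list of data to be assessed is "Effect of endoscopist experience on potential gain from using EndoRings". Experience is not defined, and no analysis is attached to the item.
- **Randomization.** After screening and consent, "the subject will be randomized in a 1:1 ratio. Randomization outcomes include the Standard Colonoscopy or the EndoRings Colonoscopy". No stratification factor, blocking, sequence method or concealment is stated, nor the point at which the performing endoscopist is settled.
- **Statistical Analysis & Sample Size.** "The primary analysis compares the adenoma detection rate between the EC group and the SC group", by a two-group chi-square at one-sided 0.05. The assumed rates "would be 25% with SC and 35% with EC colonoscopy" lead to 259 per group. There is no endoscopist term and no device-by-experience analysis.

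**The concern.** Item 10 shows that the investigators expect the gain to vary with the operator, yet neither the allocation nor the analysis mentions the operator. Three things follow, of unequal weight.

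1. The device sits on the tip of the scope, so the operator cannot be masked. If the arm can influence who does the procedure, the arms are no longer randomized with respect to skill.
2. If operators differ in baseline ADR, a pooled test leaves that variation in the error term, and chance imbalance in operator mix adds to it. Planned power is only just 80%.
3. Item 10 needs an EC-minus-SC contrast at each experience level. The plan gives neither the levels nor the analysis, and nothing stated assures a balanced split of arms within low-volume operators.

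**Working it through.** **1. The plan's own figure.** Inputs from the sample size section: 25% and 35%, one-sided 0.05, 80% power. With pooled variance and no continuity correction:

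n = [1.645 × √(2 × 0.30 × 0.70) + 0.842 × √(0.25 × 0.75 + 0.35 × 0.65)]² / 0.10² = (1.066 + 0.542)² / 0.01 ≈ 258.6, so 259 per group.

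Power at 259 is 80.05%. The figure reproduces, and endoscopist stratification would not change it.

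**2. Operator independent of arm: is the pooled test valid?** Assumed, since the plan gives no operator data: five endoscopists with about 104 patients each, baseline ADRs of 15, 20, 25, 30 and 35%, and 1:1 assignment without regard to operator. The SD of operator ADR across patients is about √0.005 = 0.071. Chance imbalance in operator mix therefore shifts the ADR difference with SD 0.071 × √(2/259) = 0.0062, or 0.6 points. In 20,000 simulated trials:

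- mean difference 0.000 under no effect and 0.100 under a true 10-point effect;
- SD of the operator-mix shift 0.6 points, with 95% of trials within about 1.2 points;
- one-sided type I error 5.2% with the pooled test;
- power 80.3% pooled and 81.1% with a Mantel-Haenszel (MH) test by endoscopist.

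The shift is small beside the total SD of the estimated difference, 3.8 points.

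**3. Power under wider operator spread.** Assumed: 518 patients, 6 or 10 operators with uneven volumes, SC ADR 25%, odds ratio 1.615.

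| Log-odds SD | Operators | Simple assignment, pooled test | Stratified assignment, MH test | Gain (points) |
|---|---|---|---|---|
| 0.4 | 6 | 78.0% | 79.3% | 1.3 |
| 0.4 | 10 | 78.7% | 79.4% | 0.7 |
| 0.7 | 6 | 75.0% | 77.1% | 2.1 |
| 0.7 | 10 | 73.9% | 77.6% | 3.7 |

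These come from 6,000 runs per setting, with a simulation error of about 0.5 points per estimate. A repeat with 20,000 runs gave gains of about 0.6 to 1 point at SD 0.4 and about 3 points at SD 0.7.

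The table changes two things at once. With MH used under both assignments (40,000 runs), simple against stratified gave 78.6% against 79.4% (6 operators) and 79.0% against 79.2% (10) at SD 0.4. At SD 0.7 it gave 77.3% against 77.8% and 77.1% against 78.1%. Stratified randomization alone is thus worth at most about 1 point; at SD 0.7 much of the gain comes from the adjusted analysis.

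**4. Operator chosen after the arm is known (hypothetical).** If 20% of one arm went to operators whose ADR differs by 10 points, the bias is 0.20 × 10 = 2 points; at 10% of the arm it is 1 point. With 25% in both arms, SE = √(2 × 0.25 × 0.75 / 259) = 0.0381. One-sided type I error when the shift favours EC:

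- 1 point: 1 − Φ(1.645 − 0.010/0.0381) = 1 − Φ(1.38) ≈ 8%;
- 2 points: 1 − Φ(1.645 − 0.020/0.0381) = 1 − Φ(1.12) ≈ 13%.

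**5. Item 10.** Assume the 518 patients split evenly into two experience levels, 129.5 per arm in each. The variance of one EC-SC difference is (0.1875 + 0.2275)/129.5 = 0.00320. The SE of the difference between two such gains is √(2 × 0.00320) = 0.080, and the 95% half-width is 1.96 × 0.080 = 0.157, about ±16 points. Power for a 10-point difference in gain is about 24% two-sided. This already assumes perfect balance.

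**6. Arm splits within operators.** Under simple assignment, the chance of a 60:40 or worse split is 50% with 20 patients, 36% with 30 and 20% with 50. At the average volumes implied by 10 or 6 operators (518/10 ≈ 52; 518/6 ≈ 86) it is about 13% and 7%. A 60:40 split raises the variance by 0.25/(0.6 × 0.4) = 1.04, that is, 4%.

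**The case against.** The strongest reply is that this is largely a design preference. Randomization already balances operator skill in expectation, the pooled test holds its level, and stratified allocation by itself buys at most about 1 point of power. Lopsided splits matter mainly for operators well below the average volume, and even 60:40 costs little. All of that stands.

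Three stronger readings are tempting, and the documents do not support them.

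- *That a single overall list deliberately ignores the endoscopist.* The Randomization section gives a ratio and a time point and is otherwise silent. Stratification is unstated, not excluded.
- *That operator skill confounds the device effect.* With the operator independent of the arm, only chance imbalance remains, and the test's error rate already covers it. Systematic mixing needs the operator to be chosen with the arm known. No section describes that, and the 20% and 10-point inputs in step 4 are not trial data.
- *That unstratified randomization is what defeats item 10.* Patients of each operator are still randomized, so the EC-SC contrast within an experience level is valid. What limits item 10 is sample size, together with the missing definition and analysis.

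The objection does not dispose of the timing gap. In a trial where the operator sees the arm and the endpoint depends on the operator, the plan leaves open a route to bias that one sentence would close. Nor does it explain why the primary test should leave out a factor that the protocol itself singles out.

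**Conclusion.** The point holds as a cheap improvement; it does not show that the primary comparison is invalid. With the operator independent of the arm, the ADR comparison is unbiased, its type I error stays at about 5%, and the loss is about 1 to 3 points of power for an assumed between-operator log-odds SD of 0.4 to 0.7. If operators do not differ, there is essentially no loss. If the operator could be chosen after the arm is known, a shift of 1 to 2 points favouring EC would take the one-sided error to about 8% to 13%; this shows why the timing should be fixed and is not an estimate of what will happen. Item 10 can support only a wide interval, about ±16 points under an even split, and stratification does not narrow it. Operator number, volume, ADR spread and experience split are all assumptions.

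**What to change.** - Record the performing endoscopist before the allocation is opened.
- Stratify the 1:1 randomization by endoscopist, with concealed, varying block sizes.
- Make the primary ADR test a Mantel-Haenszel (or equivalent) test stratified by endoscopist. If the allocation cannot be changed, this step alone still recovers much of the loss at the higher operator spread.
- For item 10, define the experience levels in advance, report the EC-SC difference within each, and label the device-by-experience interval as estimation only.

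The cost is a changed randomization list and a few sentences of text, with no extra patients or procedures; 259 per group stands. The operator must be known at allocation. Blocks within an unmasked operator are partly guessable, which varying sizes limit but do not remove. If the safeguards already exist in practice, stating them is enough for the allocation part.

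### Is the 80% power claim unsound because it rests on a one-sided 0.05 chi-square test?

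*Combined protocol and SAP*

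**What the plan says.** Everything on this point in the combined protocol and SAP is in two places.

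- **Statistical Analysis & Sample Size.** The comparison is described only in general terms: "The primary analysis compares the adenoma detection rate between the EC group and the SC group". The planning rates follow: "the proportion of patients with at least one adenoma would be 25% with SC and 35% with EC colonoscopy". The test, its level and the power claim are then given in one statement: "A two group Chi-Square test with a 0.05 one-sided significance level will have 80% power to detect a difference of 10% ADR". The section puts the matching odds ratio at 1.615 and the size at 259 per group, 518 in all.
- **Objectives** and **Introduction**. The aim is directional: the trial is meant to establish a device that raises adenoma detection relative to a standard colonoscope.

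The plan does not write out null and alternative hypotheses, gives no reason for choosing one-sided 0.05, and mentions no confidence interval. In **Methods**, slippage and "Difficulty intubating with Endorings™" are listed under equipment problems, and cecal intubation rate is a separate outcome.

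**The concern.** Three features make the statement look weak.

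1. One-sided 0.05 has the same critical value as two-sided 0.10. It permits a false claim of benefit 5% of the time, against 2.5% in that direction for a two-sided 0.05 test.
2. The Pearson chi-square statistic is a squared quantity, and software normally reports a two-sided p-value for it. An analyst who took that default at 0.05 would have roughly 10 points less power than the protocol states.
3. A rule that rejects only when EndoRings does better cannot declare that it does worse. Slippage or difficult intubation might be thought to reduce detection.

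If this amounted to a defect, either the trial's claim of benefit would rest on an error rate it should not use, or its power would be overstated by 10 points.

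**Working it through.** **Inputs** (Statistical Analysis & Sample Size; allocation from Randomization): p1 = 0.25, p2 = 0.35, difference 0.10, 1:1 allocation, n = 259 per group, one-sided level 0.05, power 80%. The mean rate is (0.25 + 0.35)/2 = 0.30. Normal quantiles: 1.645 (one-sided 0.05), 1.960 (two-sided 0.05), 0.842 (80% power).

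**Step 1: reproduce the plan's figure.** Pooled-variance formula without continuity correction:

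n = [z_α √(2·0.30·0.70) + z_β √(0.25·0.75 + 0.35·0.65)]² / 0.10²

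The square roots are √0.42 = 0.6481 and √0.415 = 0.6442.

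- One-sided 0.05: (1.645 × 0.6481 + 0.842 × 0.6442)² / 0.01 = (1.0660 + 0.5422)² / 0.01 = 258.6, so **259 per group**, 518 in total.
- Power at 259: Φ[(0.10 × √259 − 1.0660) / 0.6442] = Φ(0.843) = **80.05%**. Exact binomial enumeration of the same rule gives 80.0%.
- Odds ratio: (0.35/0.65) / (0.25/0.75) = **1.615**.

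All the figures in the sentence reproduce under the test it describes.

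**Step 2: where the 70% comes from.** Put 1.960 in place of 1.645.

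- Power at 259: Φ[(1.6093 − 1.2702) / 0.6442] = Φ(0.526) = **70.1%** (exact 70.3%).
- Size for 80% power: (1.2702 + 0.5422)² / 0.01 = 328.5, so 329 per group, 658 in total.
- If all 569 planned patients were evaluable (284.5 per group), two-sided power would be 74.1%.

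These figures are correct, but they describe a different test from the one in the plan.

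**Step 3: is a one-sided chi-square test well defined?** For a 2x2 table the Pearson statistic is the square of the pooled z statistic. The one-sided 0.05 test takes the sign of the observed difference and compares z with 1.645. Equivalently, it requires a difference favouring EndoRings and a chi-square above 1.645² = 2.71; the two-sided 0.05 cut-off is 1.960² = 3.84. The formula in Step 1 uses this rule. By exact enumeration with 25% in both groups, it rejects in the upper tail 5.02% of the time, so its error rate is essentially the stated one.

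**Step 4: what the choice changes at the margin.** With a pooled rate of 30%, the standard error of the difference is √(0.42/259) = 0.0403. The smallest significant observed gain is 1.645 × 0.0403 = 6.6 points one-sided and 1.960 × 0.0403 = 7.9 points two-sided. Under the plan's own rates, 80.05% − 70.07% ≈ 10% of trials would be significant by the first rule and not by the second. This is the price of the extra stringency. It does not show that the stated rule is invalid.

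**Step 5: the adverse direction.** If detection is equal or lower with EndoRings, the test does not reject, and the valid conclusion is that improvement was not shown. Both rates can still be estimated and reported. The documents name no decision that depends on separating no better from significantly worse, and they do not say that slippage or intubation difficulty lowers detection.

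**The case for a change.** The strongest case for changing the plan is this. Stating a lenient level openly does not justify it, and a superiority aim can be tested at one-sided 0.025. The level appears only in the power sentence, while the description of the primary comparison has no direction, hypotheses or interval. A result in the gap between the two rules is then open to dispute. For example, 26.5% against 33.5% gives z = 0.07/0.0403 = 1.74 and one-sided p = 0.041, yet its two-sided 95% interval runs from about −0.9 to +14.9 points.

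Part of this stands. The plan gives no reason for one-sided 0.05 and leaves the direction to be inferred, and an interval would make a marginal result easier to read. These are gaps in detail.

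The step from there to a defect does not stand. The power sentence names the level and the test together, so reading the test as two-sided means setting aside one of its words. Nothing in the documents requires a two-sided analysis. Nor is the change cheap. At 259 per group it leaves power at 70%, below the trial's own 80% target. Keeping 80% would mean either planning around about 36.3% with EndoRings (a gain of 11.3 points), a rate the plan never assumed, or recruiting 658 evaluable patients. With the 10% drop-out allowance, 658 becomes 724 (658 × 1.10) to 732 (658/0.90) enrolled.

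**Conclusion.** The concern does not hold. For the test and level the plan states, 259 per group gives 80.05% power, and the 10-point shortfall arises only if a different test is substituted. The one-sided direction agrees with the stated aim, the procedure is well defined, and a null or unfavourable result can still be interpreted. Whether 5% or 2.5% is the better one-sided error rate is a question of convention and trade-off, and the documents contain no error or contradiction on it.

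This rests on three assumptions: the upper-tail direction is read from the 25% and 35% planning rates and the Objectives, since no hypotheses are written; the analysis follows the stated one-sided level; and 518 patients are evaluable, which is the number to which the stated power applies.

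### Optional refinement, not an error: the pooled chi-square is valid, but a prespecified test stratified by screening versus surveillance would use a known baseline factor at almost no cost

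*Combined protocol and SAP*

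**What the plan says.** Under Statistical Analysis & Sample Size, "The primary analysis compares the adenoma detection rate between the EC group and the SC group". One rate per arm is assumed: "It is assumed that the proportion of patients with at least one adenoma would be 25% with SC and 35% with EC colonoscopy". The test is a single unstratified comparison: "A two group Chi-Square test with a 0.05 one-sided significance level will have 80% power", with 259 per group (518 in total, 569 after the dropout allowance).

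The inclusion criteria admit two kinds of patient: "Screening or Surveillance Colonoscopy". Randomization comes only "Once a patient has been screened to ensure inclusion and exclusion criteria have been met" and consent is given. It is described only as a ratio: "the subject will be randomized in a 1:1 ratio". Neither section names a stratum or covariate, and the mix of indications and the ADR within each are not given.

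The same statistical section adds: "Interim analysis will be performed after the 200th patient is enrolled to assess device performance and protocol amendment".

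**The concern.** Whether a patient comes for screening or surveillance is a baseline fact that the device cannot affect, and it is settled when eligibility is checked. It may also predict whether an adenoma is found. If it does, comparing arms within each indication removes some between-patient variation from the test and gives slightly more power from the same patients. The planned power is 80.05%, so there is almost no margin at the design sample size.

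Only a little precision is at stake. Timing matters because the interim look may lead to a protocol amendment. A change of primary test made after outcomes by arm have been seen could be data-driven.

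**Working it through.** **Inputs from the plan.** Standard arm 25%, EndoRings arm 35%, one-sided 0.05 (z = 1.645), 80% power (z = 0.842), 259 per arm, unstratified 1:1 allocation. **Assumed:** the odds ratio (OR) for an adenoma by indication, and a surveillance share of 30% to 70%. In every case the overall rates are held at 25% and 35%.

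**1. The plan's own figure.** With mean rate 0.30:

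n = [1.645 × √(2 × 0.30 × 0.70) + 0.842 × √(0.25 × 0.75 + 0.35 × 0.65)]² / 0.10² = [1.645 × 0.6481 + 0.842 × 0.6442]² / 0.01 = 258.6, so 259.

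Power at 259 is 80.05%. The plan's figure reproduces.

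**2. Stratified test, large-sample formula.** Let w be the share of each indication, pS and pE its rates in the two arms, and p̄ their mean. Then power = Φ[(D − 1.645√V0)/√V1], where
- D = Σ (259w/2)(pE − pS) = 129.5 × 0.10 = 12.95
- V0 = Σ (259w/2) p̄(1 − p̄)
- V1 = Σ (259w/4)[pS(1 − pS) + pE(1 − pE)]

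*Indication not predictive (OR 1.0).* V0 = 129.5 × 0.21 = 27.195 and V1 = 64.75 × 0.415 = 26.871. Power = Φ[(12.95 − 8.578)/5.184] = Φ(0.843) = 80.05%, the same as the pooled test.

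*OR 2.23, 30% surveillance.* Rates are 20.2% and 36.1% with standard colonoscopy, and 29.4% and 48.1% with EndoRings.
- V0 = 129.5 × (0.7 × 0.1865 + 0.3 × 0.2438) = 26.38
- V1 = 64.75 × (0.7 × 0.3689 + 0.3 × 0.4804) = 26.05
- Power = Φ[(12.95 − 8.448)/5.104] = Φ(0.882) = 81.1%, a gain of about 1.1 points.

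**3. Simulation** (400,000 trials per case; gains over the pooled test, 30% to 70% surveillance):

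| Assumed OR by indication | Gain, uncorrected CMH |
|---|---|
| 1.0 | 0.0 points |
| 1.65 | about +0.4 to +0.5 |
| 2.23 | about +0.9 to +1.1 |

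Type I error of the stratified test stays at 5.0%. For scale, the pooled formula gives 80.45% at 262 per arm and 81.23% at 268, so these gains are worth roughly 3 to 9 patients per arm. The 90% interval for the risk difference barely narrows: its half-width is 6.57 points crude, against 6.52 (OR 1.65) or 6.46 (OR 2.23) by Mantel-Haenszel.

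**4. Continuity correction.** The usual correction takes 0.5 from D. At OR 1.0, power = Φ[(12.95 − 0.5 − 8.578)/5.184] = Φ(0.747) = 77.2%, so 80.05 − 77.2 ≈ 2.8 points are lost. Simulated power with the correction is 77.1% to 78.4% for OR 1.0 to 2.23. All of these are below the planned 80%.

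**5. Worst case tried.** Suppose the effect of indication on the log-odds has the same size but the opposite sign in the EndoRings arm. At OR 2.23 and 70% surveillance, the pooled test has 80.06% power and the CMH test 79.91%, a loss of 0.15 points.

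**The case against.** The case against is that nothing here is wrong. An unadjusted chi-square is a standard primary test for a randomized binary endpoint, and the plan's test, level, rates and sample size agree with one another. This stands, and it is why the point is offered as an option.

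The gain also has no support in the documents, which do not say that indication predicts ADR. About one point needs an assumed difference of roughly 16 ADR points between indications (20% against 36%). Dropout matters more: if none of the 569 were lost, about 284 per arm would give 83.2% under the same formula. This stands too, and the gain can be stated only as a conditional range.

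The cost is not strictly nil. Indication is missing from the data items listed under Methods, and eligibility is met by either indication, so the plan must say that it is recorded. The test is also not free of loss in every case, as step 5 of the working shows.

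Two stronger readings are tempting. A reader might infer that pooling two kinds of patient biases the comparison or inflates the error rate. It does not: allocation is random and the pooled test holds its level. A reader might also infer that operators should be strata, since several take part. The documents give neither the number of operators nor the time at which they are assigned. With an assumed six operator groups crossed with indication, up to about 0.7 points are lost when there is no spread.

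**Conclusion.** The point holds as an optional improvement. The planned analysis is valid and its sample size is correct for the stated assumptions. Using indication would add 0.0 power points if it does not predict ADR, and up to about 1.1 points at the larger of the two odds ratios examined. That upper figure is not a ceiling: an assumed gap of 20 ADR points gives +1.5 to +2.2. The documents cannot show where in this range the trial lies. The largest loss found is about 0.2 points, under a reversed interaction that is extreme. The case for the change rests on low cost and little downside, provided that the test is uncorrected and fixed before outcomes by arm are seen.

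**What to change.** Before any look at outcomes by arm, including the interim after the 200th patient, amend Statistical Analysis & Sample Size to state:

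- The primary test is a Cochran-Mantel-Haenszel test **without continuity correction**, one-sided 0.05, stratified by indication (screening or surveillance).
- Indication is recorded for every patient before randomization.
- The Mantel-Haenszel risk difference is reported with a two-sided 90% confidence interval, which matches the one-sided 0.05 level.
- The crude chi-square is kept as a sensitivity analysis.
- Operator is not a stratum in the primary test.

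If outcomes by arm have already been seen, keep the crude chi-square as primary and report the stratified test as a sensitivity analysis only.

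The cost is a few lines of protocol text and one recorded item per patient. No extra patients or procedures are needed, and 259 per group stands.

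### Does sizing the trial for 10% drop-out, with withdrawal by the investigator allowed, bias the adenoma detection rate in favour of EndoRings?

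*Combined protocol and SAP*

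**What the plan says.** Under Randomization, allocation is 1:1 and follows eligibility and consent: "Once a patient has been screened to ensure inclusion and exclusion criteria have been met and has provided consent for participation". Under Statistical Analysis & Sample Size, "The primary analysis compares the adenoma detection rate between the EC group and the SC group". The assumption is that "the proportion of patients with at least one adenoma would be 25% with SC and 35% with EC colonoscopy", tested by "A two group Chi-Square test with a 0.05 one-sided significance level". That gives 259 per group, 518 in all, for 80% power, and then: "The final sample size will be 569 after adding the 10% expected drop-out rate".

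Under Data Integrity and Safety, subjects may leave of their own accord, and "the Investigator may decide for reasons of medical prudence, to withdraw a subject". In either case the date and reason go into the CRF, with the investigator's view on whether the withdrawal was related to the study interventions. No time limit relative to allocation or procedure is given.

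The Methods section lists the data to be assessed from each colonoscopy. Cecal intubation rate is one item. Equipment problems are another, with slippage of the device and "Difficulty intubating with Endorings™" as sub-items.

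The plan does not name an analysis population, does not say how ADR is scored when a procedure is incomplete, converted or withdrawn, and does not mention blinding.

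**The concern.** ADR is read from one procedure done after randomization, and no follow-up visit is described at which it could go missing. An allowance of 10% therefore invites the question of who is expected to drop out. It has a purpose only if some enrolled patients are not expected to contribute to the primary test.

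Two features suggest that losses might differ by arm. Slippage and difficulty intubating with the device can occur only in EC. The device also sits on the tip of the scope, so the person doing the examination can presumably see the arm, and investigators do the examinations. If EC examinations that went badly were withdrawn and left out, and if they had found fewer adenomas than average, the remaining EC patients would show a raised ADR. The comparison would no longer be between the groups as randomized, and a device with no effect could be declared superior too often.

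**Working it through.** **The plan's own figures.** Inputs from Statistical Analysis & Sample Size: 25% and 35%, one-sided 0.05, 80% power. With pooled variance and no continuity correction,

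n per arm = [1.645 × √(2 × 0.30 × 0.70) + 0.842 × √(0.25 × 0.75 + 0.35 × 0.65)]² / 0.10² = 258.6, rounded up to 259.

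Power at 259 per arm is 80.05%, and the odds ratio is (0.35/0.65)/(0.25/0.75) = 1.615. Both match. The final figure is 518 × 1.10 = 569.8, truncated to 569. Losing 10% of 569 leaves 512, with power 79.6%, so the sample size is sound for its purpose.

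**Bias if lost patients are dropped.** Let d be the share of an arm lost and q the ADR those patients would have had. With a full-arm ADR of 25%, the observed ADR is (0.25 − d × q)/(1 − d). The documents give neither d nor q, so both are assumptions. Arms are 285 EC and 284 SC, with no true effect and a one-sided 0.05 test.

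*All losses in EC, none in SC:*

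| EC lost | q | Observed EC ADR | Type I error |
|---|---|---|---|
| 5% | 10% | (0.25 − 0.005)/0.95 = 25.8% | 7.7% |
| 10% | 15% | (0.25 − 0.015)/0.90 = 26.1% | 8.9% |
| 10% | 10% | (0.25 − 0.010)/0.90 = 26.7% | 11.4% |
| 10% | 0% | 0.25/0.90 = 27.8% | 18.0% |
| 10% | 25% | 25.0% | 5.0% |

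If 28 EC patients are lost with q = 50%, the observed ADR is (285 × 0.25 − 28 × 0.50)/257 = 22.3% and the rejection probability falls to about 1%. If the plan's whole allowance of 57 fell on EC, the rejection probability would be about 25% at q = 10% and 47% at q = 0.

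*Losses in both arms, moderately unequal:*

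- 6% EC and 4% SC, q = 10%: EC (0.25 − 0.006)/0.94 = 25.96%, SC (0.25 − 0.004)/0.96 = 25.63%; type I error about 6.0%. At q = 15% it is 5.6%.
- 12% EC and 8% SC, which together make up the plan's 10% of all patients, q = 10%: EC (0.25 − 0.012)/0.88 = 27.05%, SC (0.25 − 0.008)/0.92 = 26.30%; type I error about 7.3%. At q = 15% it is about 6.5%.
- Equal losses with the same q in each arm: both rates move together and the error stays at 5%.

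**What the text supports.** Upward bias needs (a) more losses in EC, (b) those patients left out of the denominator and (c) q below the arm's ADR. The plan states none of the three. On (a), the Methods section lists slippage, difficulty intubating and cecal intubation rate as data to record, not as grounds for withdrawal, and the last applies to both arms. On (b), no sentence removes anyone. A cecal intubation rate assessed from each colonoscopy can be calculated only if incomplete examinations stay in the dataset. On (c), low yield in a failed examination is plausible, but the documents do not say so.

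**The case for a change.** The best case for acting is that the primary result rests on an unwritten rule and that writing it down costs almost nothing: analyse every randomized patient whose colonoscopy starts, in the assigned arm, scoring ADR on what was found. The drop-out allowance does imply that some patients will not be analysed. Recording the reason for a withdrawal does not settle who is counted. Less colon is seen when an examination fails to advance, so below-average detection is the natural direction. The 10% EC-only scenarios use about 28 lost patients, half of the 57 that the allowance covers.

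Much of this stands. The omission is real, the arithmetic is right, and an explicit sentence would be good practice. It does not show that the plan goes wrong. Adding 10% is routine and fits losses before the procedure, such as consent withdrawn or an examination that never starts. The remedy would exclude those patients too, so enrolling 569 to analyse roughly 518 is compatible with it. Withdrawal is limited to medical prudence and is documented with its relation to the intervention, so losses can be tabulated by arm and reason.

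Nor is the remedy always cheap in power. Suppose 35% holds only in completed EC examinations. With 5% failing at 10% ADR, the EC rate is 0.95 × 0.35 + 0.05 × 0.10 = 33.8% and power is about 74%. With 10% failing and no adenoma found, it is 0.90 × 0.35 = 31.5% and power is about 53%. Without failures power is 83% at 285 and 284. That is no reason to exclude failures, since it reflects the device as assigned, but the cost can be more than slight.

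**Conclusion.** The concern does not call for a change. What remains is that the plan leaves the analysis population and the scoring of incomplete, converted or withdrawn procedures unstated. No stated rule produces a wrong result. The primary analysis is described as a comparison of the two groups, and an analyst would ordinarily keep started examinations in the arm to which they were randomized and score them on what was found.

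The size depends wholly on assumed loss patterns. For the scenarios with 5% or 10% of EC lost and none of SC, type I error is 7.7% to 18.0%. It is about 6% to 7% for the moderately unequal splits, 5% if losses are balanced or unrelated to detection, and below 5% if the EC patients lost had above-average detection. The high figures, up to 47% if all 57 losses fell on EC with no adenomas among them, need one-sided losses, exclusion and low yield together. The documents establish none of these. The judgement would change if the plan said that incomplete or withdrawn procedures leave the ADR denominator; it does not.
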